10.4.2 Progression Free Survival 2 (PFS2)

The second event of PFS (referred to as PFS2) is defined as the time from randomization to the second event of disease progression as assessed by the investigator, or death due to any cause. The first event of disease progression will be captured as the primary endpoint in this study and thus the second event will be the next event of disease progression as assessed by the investigator. This second event of PFS may be a documented event per RECIST guidelines or may be an event of symptomatic/clinical or CA-125 progression.

10.4.3 ORR per RECIST v1.1 as Assessed by the Investigator

The Overall Response Rate (ORR) as assessed by the investigator will be analyzed in the subgroup of patients who have measurable disease (i.e., measurable target lesions) at baseline. Both unconfirmed and confirmed response rate by RECIST v1.1 will be summarized. The confirmed response rate is defined as the proportion of patients with a confirmed CR or PR on subsequent tumor assessment at least 28 days after first response documentation. The ORR will be summarized with frequencies and proportion together with 95% confidence interval (CI) and compared between treatments by using a stratified Cochran-Mantel-Haenszel (CMH) test. In addition, the frequency and proportion of patients will be summarized for each of the unconfirmed and confirmed response categories:

- CR
- PR
- Stable disease (SD)
- Progressive disease (PD)
- Not evaluable (for example, discontinuation or death before first tumor assessment)

10.4.4 Duration of Response (DOR) per RECIST v1.1 as Assessed by the Investigator

The Duration of Response (DOR) as assessed by investigator will be analyzed in the subgroup of patients who have measurable disease (i.e., measurable target lesions) at baseline and have a confirmed response by RECIST v1.1. DOR for any confirmed RECIST CR or PR will be measured from the date of the first response until the first date that PD is documented. DOR will

be summarized as a time to event variable. For patients who continue treatment post-progression, the first date of progression will be used for the analysis. Any patients with an ongoing response will be censored at the date of the last post-baseline scan.

The Kaplan-Meier methodology will be used to summarize DOR. If able to be estimated, the 50th (median) together with a 95% CI, will be presented. The stratified log rank test comparing the treatment groups will also be presented. The number of patients with PD events and the number of censored patients will also be presented.

10.4.5 Change from Baseline in Sum of the Diameters of Target Lesions as Assessed by the Investigator

The change from baseline in sum of diameters of target lesions as assessed by the investigator will be analyzed in the subgroup of patients who have measurable disease (i.e., measurable target lesions) at baseline. The largest percent decrease from baseline in the sum of the diameters of target lesions as identified by RECIST v1.1 will be displayed graphically using a waterfall plot. This analysis will be based on the investigator assessed tumor responses and only presented for patients with measurable disease at baseline and one valid post-baseline evaluation of the target lesions.

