### 11.2 Statistical Methods

#### 11.2.1 General Considerations

Variables registered on a continuous scale will be presented using the following descriptive statistics: N, mean, standard deviation, median, minimum and maximum. Continuous variables may also be presented using frequencies and percentages among appropriate categorizations. Categorical variables will be presented using frequencies and percentages. The Kaplan-Meier methodology will be used to summarize time-to-event variables. The number of patients with events and the number of censored patients will also be presented. The stratified logrank test will be used to compare the time-to-event distributions between the randomized treatment groups. In addition, the Cox proportional hazards model will be used to estimate the HR between the randomized treatment groups.

The primary and key secondary endpoints will be tested among the tBRCA and all HRD subgroups, and all randomized patients, using an ordered step-down multiple comparisons procedure. Investigator determined PFS (invPFS) in the tBRCA subgroup will be tested first at a one-sided 0.025 significance level. If invPFS in the tBRCA subgroup is statistically significant, then invPFS will be tested in the all HRD subgroup followed by invPFS in all randomized patients. Continuing in an ordered step-down manner, the PRO of disease symptoms utilizing the FOSI-18 DRS-P subscale will be tested at the one-sided 0.025 significance level in the tBRCA, all HRD, and all randomized patients subgroups and then for the remaining key secondary endpoints of PRO utilizing the FOSI-18 total score and OS. Once statistical significance is not achieved for one test the statistical significance will not be declared for all subsequent analyses in the ordered step-down procedure.

PFS by IRR will be evaluated as a stand-alone secondary endpoint.

All data will be used to their maximum possible extent but without any imputations for missing data.

All statistical analyses will be conducted with the SAS® System, v9.1 or higher.

Unless otherwise specified, baseline is defined as the last measurement on or prior to the first day of study drug administration.

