### **11.2.7.4 Duration of Response**

The DOR is measured from the time measurement criteria are met for CR/PR per RECIST v1.1 criteria ([Appendix B](#)), as assessed by both the investigator and IRR, until the first date that recurrent or progressive disease (PD) is objectively documented. The DOR will be summarized with descriptive statistics. Only patients with a response will be included in the summary.

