10.4 Exploratory Endpoints

Exploratory endpoints will be presented separately for the three nested analysis populations (i.e., tBRCA, HRD, and ITT population). The exploratory endpoints include change in CA-125 level, tumor response, and DOR in patients who had measurable disease per the investigator at baseline. The purpose of the exploratory endpoint is to further explore the efficacy. No multiple adjustment is performed for these analyses.

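### The SAP's log-rank test of duration of response compares responders only, so its p-value is not protected by randomization and can point the wrong way

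*SAP*

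**What the plan says.** SAP 10.4.4 analyses DOR in patients who have measurable target lesions at baseline and who "have a confirmed response by RECIST v1.1". The duration is "measured from the date of the first response until the first date that PD is documented". It is summarized by Kaplan-Meier, with the median and its 95% confidence interval where estimable. The section then adds the between-arm test: "The stratified log rank test comparing the treatment groups will also be presented". It gives no caveat about how responders come to be selected.

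Protocol 11.2.7.4 says of the same endpoint: "The DOR will be summarized with descriptive statistics. Only patients with a response will be included in the summary". It names no test. Protocol 11.2.1 contains a general rule: "The stratified logrank test will be used to compare the time-to-event distributions between the randomized treatment groups". That rule does not mention DOR.

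SAP 10.4 classes DOR as exploratory and states: "No multiple adjustment is performed for these analyses". It also states: "Exploratory endpoints will be presented separately for the three nested analysis populations". The test would therefore be reported for tBRCA, HRD and ITT. SAP 10.4.3 separately compares the response rate between arms with a stratified Cochran-Mantel-Haenszel (CMH) test in all patients with measurable disease at baseline.

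**The concern.** Confirmed response is observed after randomization. The SAP itself treats it as something treatment may change, because it compares response rates between arms. If it does change, the responders in the two arms are different kinds of patient. The rucaparib responders would include some who would not have responded on placebo, and the placebo responders would have no counterpart to them. The clock also starts at first response, not at randomization.

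A log-rank test on these two groups mixes two things: any effect on how long a response lasts, and the change in who responds. A drug that turns non-responders into short-lived responders can appear to shorten response while harming nobody. A p-value printed beside the curves gives the contrast a standing that it does not have. What is at stake is the reading of one exploratory result in the study report.

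**Working it through.** The documents state no response rate, response duration, responder count or power for DOR. There is no figure of the plan's own to reproduce, and every clinical input below is an assumption.

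**1. Direction and size of the selection effect**

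Assumed inputs, among patients with measurable disease:
- 15% respond on either arm, with median duration 12 months on both (always-responders).
- A further 20% respond on rucaparib only, with median *m* months.
- Durations are exponential.

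Rucaparib responders are then 15/35 = 3/7 always-responders and 20/35 = 4/7 extra responders. At the start of response, the hazard ratio of rucaparib to placebo responders is

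3/7 + (4/7) × (12/*m*).

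It then drifts as the shorter responders leave the risk set. The Cox estimate averages over follow-up. It was obtained by large-sample simulation with uniform censoring at 12 to 30 months.

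| Extra responders' median *m* | Hazard ratio at start | Cox hazard ratio, responders only |
|---|---|---|
| 6 months | 3/7 + 8/7 = 1.57 | about 1.46 |
| 9 months | 3/7 + 16/21 = 1.19 | about 1.18 |
| 12 months | 1.00 | 1.00 |
| 15 months | 3/7 + 16/35 = 0.89 | about 0.88 |

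No patient's response is shorter on rucaparib than on placebo in any row. The answer depends on who the extra responders are. With only 5% extra responders at *m* = 6, the hazard ratio is about 1.2.

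**2. The same data on a randomized basis (*m* = 6)**

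Median DOR among rucaparib responders solves (3/7)·2^(−t/12) + (4/7)·2^(−t/6) = 0.5. With x = 2^(−t/12) this is (4/7)x² + (3/7)x − 0.5 = 0, so x = 0.633 and t = 7.9 months. The placebo median is 12 months, so this summary favours placebo.

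Mean time in response over all patients with measurable disease, non-responders counted as zero:
- Placebo: 0.15 × 12/ln 2 = 2.60 months.
- Rucaparib: 2.60 + 0.20 × 6/ln 2 = 2.60 + 1.73 = 4.33 months.

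This summary favours rucaparib. The two point in opposite directions on the same patients.

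**3. At the trial's size**

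From the SAP: about 540 patients, randomized 2:1. Assumed:
- 30 to 60% have measurable disease.
- Response is 20 to 40% on rucaparib and 10% on placebo, at month 3.
- Always-responders' median DOR is 10 months on placebo and 12 on rucaparib; rucaparib-only responders' is 5 months.
- Median progression-free survival (PFS) is 4 months on placebo for patients who do not respond there. On rucaparib it is 6 months for those who still do not respond.
- Censoring is uniform at 6 to 24 months. There were 2,000 simulated trials per scenario, and the log-rank test was unstratified.

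Every patient type gains from rucaparib. Across the nine scenarios:
- The PFS hazard ratio in the measurable-disease subset was 0.59 to 0.66, the right direction.
- The DOR hazard ratio among responders was 1.26 to 1.50, and exceeded 1 in 65 to 87% of trials.
- The DOR test was significant against rucaparib in 3.5 to 16.1% of trials (nominal 2.5% per side) and in its favour in 0.4 to 2.4%.

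One contrast isolates the cause. Take 40% measurable disease and always-responders going from 10 to 15 months. With response 30% against 10%, the DOR hazard ratio is about 1.32. With response 30% in both arms, and so no selection, it is about 0.64. The reversal comes from the change in who responds.

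**4. Sparsity**

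Placebo patients: 540/3 = 180. With 30 to 60% measurable, 54 to 108. With 10 to 15% responding (assumed), about 5 to 16 placebo responders in ITT. The stratified test uses 3 × 2 × 2 = 12 strata. Even apart from selection there is little for it to work with, and there is less in tBRCA and HRD.

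**The case against.** **The protocol's general rule may already cover the test.** The SAP treats DOR as a time-to-event variable, Protocol 11.2.1 sets the log-rank test for such variables, and the SAP says that it adds detail to the protocol. A reader might infer from Protocol 11.2.7.4 that the SAP contradicts the protocol. The documents do not support that. The DOR section plans description without excluding a test, and the general sentence can be read either way. It speaks of the randomized groups, which confirmed responders are not, so it gives weak cover; but the protocol is ambiguous, not breached. The SAP was also written against the protocol through Amendment 3, whereas the protocol text here is at Amendment 5, so the DOR wording then in force cannot be seen.

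**The illustration rests on assumptions.** This stands. The size and sign depend on the extra responders' duration, and at 15 months the contrast favours rucaparib. A reader might infer that the test will penalize rucaparib here. That is possible, not shown: nothing in the documents says how many extra responders there are or how long they respond.

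**The consequences are contained.** This also stands. DOR is exploratory and outside the step-down procedure, and a comparison of response rates that keeps non-responders is already planned. This limits the weight of the point but does not make the responder-only test valid.

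**Conclusion.** The point holds, at low severity. As written, the SAP produces a p-value for DOR in each of three populations from groups formed after randomization by an outcome that treatment may affect. That p-value does not estimate a treatment effect and can mislead in either direction. Under the assumed inputs, the responder-only hazard ratio runs from about 1.46 to 0.88 as the extra responders' median runs from 6 to 15 months, with nobody losing response time. The reasoning needs only that treatment may change who responds; the numbers need the assumed rates and exponential durations.

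A reader might also infer that the trial's efficacy claims are weakened. They are not: the primary endpoint and the step-down tests do not use this comparison.

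**What to change.** Delete the log-rank sentence from SAP 10.4.4. Keep the Kaplan-Meier median with 95% confidence interval per arm, which that section already provides, and label it as description of responders only.

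For a comparison between arms, rely on the response rate by stratified CMH test in SAP 10.4.3. Its population is fixed at baseline, so the groups remain those formed by randomization. Optionally, add time in response in that same population, with non-responders counted as zero and the time horizon stated in advance.

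The deletion costs one sentence and one exploratory p-value. The optional analysis costs one extra curve or summary and needs no new data.

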10.4.6 Patient Reported Outcome of EQ-5D

Analyses of changes and/or percent changes from baseline will be analyzed for each scheduled post-baseline visit and for the final visit for EQ-5D VAS. Patients that do not have both a baseline measurement and at least one post-baseline measurement will not be included.

At a given visit, the change and/or percent change from baseline will be compared between the randomized treatment groups using an ANCOVA using the treatment as a categorical factor and baseline measurement for the parameter as a continuous covariate.

10.4.7 Exploratory Endpoint: Association Between the Change from Baseline in CA-125 Measurement and invPFS

The association between the change from baseline in CA-125 and invPFS will be analyzed by adding the maximum decrease from baseline in CA-125 to the stratified Cox proportional model as a covariate in the model. The change or percent change will be analyzed both as a continuous variable and as a categorical variable depending on the data distribution.

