--	--

	
of contraception (failure rate < 1% per year) with their male partners during treatment and for 6 months following the last study drug dose.
 
No waivers of these inclusion or exclusion criteria will be granted by the investigator and the sponsor or its designee for any patient enrolled into the study.

Study Treatment	
Eligible patients will be randomized 2:1 to receive rucaparib (600 mg twice a day [BID]) or placebo. Randomization will occur by a central randomization procedure using an Interactive Voice Response System/Interactive Web Response System (IVRS/IWRS). The following will be included as randomization stratification factors at study entry to ensure treatment groups are balanced:
 
 
• HRD classification (tBRCA, nbHRD, or biomarker negative) by the ICTA (Appendix A).
 
• Interval between completion of the penultimate platinum-based regimen and disease progression (6 to 12 or >12 months) by radiologic assessment
 
• Best response to the most recent platinum-based regimen (CR [defined as complete radiologic response by RECIST or PR [defined as partial response by RECIST and/or a GCIG CA-125 response]). All responses require that CA-125 be <ULN.
 
 
Randomization to study treatment must occur within 8 weeks following a patient's last dose of platinum-based chemotherapy. Study drug will be taken orally twice daily (12 hours apart) with at least 8 oz (240 mL) of water. Study drug may be taken with an empty stomach or with food.
 
Patients will take study drug twice daily for continuous 28-day cycles until disease progression by RECIST as assessed by the investigator, or other reason for discontinuation. Treatment interruptions and/or dose reductions are permitted in the event of unacceptable toxicity.

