## **9.5 Methods of Data Collection**

Hematology, clinical chemistry, urinalysis, serum CA-125, and serum pregnancy in women of child-bearing potential will be performed locally.

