### **9.5.5.2 Tumor Markers**

CA-125 measurement will be performed at screening, on Day 1 of Cycle 1, at the start of every 3rd cycle thereafter (i.e., Day 1 of Cycle 4, Cycle 7, Cycle 10, etc.), at discontinuation of treatment, and as clinically indicated.

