1 INTRODUCTION

This document describes the statistical analyses and data presentations to be performed for the clinical study report (CSR) of Clovis Oncology protocol CO-338-014 "A Multicenter, Randomized, Double-Blind, Placebo-Controlled Phase 3 Study of Rucaparib as Switch Maintenance Following Platinum-Based Chemotherapy in Patients with Platinum-Sensitive, High-Grade Serous or Endometrioid Epithelial Ovarian, Primary Peritoneal or Fallopian Tube Cancer."

This statistical analysis plan (SAP) provides a comprehensive and detailed description of the strategy, rationale, and statistical techniques to be used to assess the efficacy and safety of rucaparib (CO-338) compared with placebo in patients with platinum-sensitive high-grade serous ovarian or endometrioid epithelial ovarian, primary peritoneal, or fallopian tube cancer who achieved a response to platinum-based therapy.

The purpose of the SAP is to ensure the credibility of the study findings by specifying the statistical approaches to the analysis of study data prior to snapshot and unblinding of treatment codes. This SAP provides additional details around the statistical analyses that are outlined in the original protocol dated 9 Sep 2013, and three protocol amendments (Amendment 1 dated 4 Nov 2014, Amendment 2 dated 9 Mar 2015, and Amendment 3 dated 7 Jul 2016).

All statistical analyses detailed in this SAP will be conducted using SAS[®] Version 9.3 or higher.

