10 EFFICACY ANALYSIS

10.1 Primary Efficacy Analysis

The primary efficacy endpoint is PFS as assessed by the investigator (invPFS). The time to invPFS will be calculated in months as the time from randomization to disease progression +1 day, as determined by RECIST v1.1 criteria² or death due to any cause, whichever occurs first.

Only scans and deaths prior to the start of any subsequent anti-cancer treatment or within 90 days of treatment end date will be included in the analysis. Patients without a documented event of progression will be censored on the date of their last tumor assessment (i.e., radiologic assessment) prior to the start of any subsequent anti-cancer treatment or within 90 days of treatment end date. Patients who withdrew without a disease progression event and do not have any post-baseline tumor assessment will be censored at date of randomization.

The stratified log rank test will be considered the primary analysis for invPFS comparing rucparib to placebo. In addition, a stratified Cox proportional hazard model will be used to calculate the hazard ratio (HR) between the treatment groups. The following randomization strata are used to estimate the treatment effect:

- HRD classification by the CTA (tBRCA, nbHRD, biomarker negative)
- Best response to most recent platinum-based regimen (CR, PR)
- Interval between completion of the penultimate platinum-based regimen and disease progression (6 to 12 months or > 12 months)

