10.4.1 Change from Baseline in CA-125 Measurement

Analyses of changes and/or percent changes from baseline for CA-125 measured by the central laboratory will be analyzed for each scheduled post-baseline visit and for the final visit. Patients who do not have both a baseline measurement and at least one post-baseline measurement will not be included in these analyses.

At a given visit, the change and/or percent change from baseline for CA-125 will be compared between the randomized treatment groups using an ANCOVA using the treatment as a categorical factor and baseline measurement for the parameter as a continuous covariate.

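### SAP 10.4.7 enters each patient's maximum CA-125 decrease as if it were known at randomization, so the exploratory CA-125/invPFS hazard ratio is open to guarantee-time bias

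*SAP*

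**What the plan says.** **Covariate.** SAP 10.4.7 analyses the association by "adding the maximum decrease from baseline in CA-125 to the stratified Cox proportional model as a covariate in the model". It asks for a continuous and a categorical version, gives no cut-points, and names no window, landmark or time-dependent coding.

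**Clock.** SAP 10.1: "The time to invPFS will be calculated in months as the time from randomization to disease progression +1 day".

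**Sampling.** Protocol 9.5.5.2 measures CA-125 at screening, on Day 1 of Cycle 1, "at the start of every 3rd cycle thereafter", and "at discontinuation of treatment, and as clinically indicated". Protocol Synopsis, Study Treatment: "Patients will take study drug twice daily for continuous 28-day cycles until disease progression by RECIST as assessed by the investigator".

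**Which values count.** SAP 10.4.7 is silent. The nearest text is SAP 10.4.1: "percent changes from baseline for CA-125 measured by the central laboratory will be analyzed for each scheduled post-baseline visit". That sentence goes on to include the final visit, which is not defined. SAP 10.4.1 also leaves out patients who lack a baseline or any post-baseline value. It governs the visit-by-visit comparison, not expressly 10.4.7.

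**Protocol request.** Protocol 11.2.7.1 wants the change from baseline related to invPFS in a Cox model and allows a kinetic measure such as a rate of change. The maximum decrease is the SAP's own choice.

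**Versions.** The SAP elaborates analyses "outlined in the original protocol dated 9 Sep 2013, and three protocol amendments", while the protocol to hand is at Amendment 5, so the 12-week interval is read from a later version. SAP 10.4.1 and Protocol 11.2.7 and 11.2.7.1 name the central laboratory. Protocol 9.5 says: "Hematology, clinical chemistry, urinalysis, serum CA-125, and serum pregnancy in women of child-bearing potential will be performed locally".

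**Status.** SAP 10.4 treats the analysis as exploratory, without multiplicity adjustment.

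**The concern.** A fixed covariate in a Cox model is treated as known at time zero. A maximum taken over follow-up is not known then. Without a stated window, the natural reading of SAP 10.4.7 is the maximum over all available follow-up. A patient who progresses at 4 months has one scheduled post-baseline value; a patient who progresses at 12 months has four. The second has more chances of a low value, so random variation alone can link a larger decrease to longer invPFS.

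At stake is the first exploratory objective in Table 1 of both documents, the relationship between CA-125 and invPFS. A reader could take an artefact as evidence that a CA-125 fall tracks benefit.

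**Working it through.** The documents give no figure for this association, so there is nothing of the plan's to reproduce. The check asks what the specified model returns when CA-125 has no relation to PFS.

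**Why the covariate moves with follow-up.** Assume log CA-125 is independent standard normal noise at baseline and at each of k later visits. The expected maximum decrease equals the expected largest of k standard normals:
- k = 1: 0
- k = 2: 1/√π = 0.56
- k = 3: 3/(2√π) = 0.85

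More visits give a larger decrease with no biology involved.

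**Why the sign can change.** Add a common upward drift of 1 noise-SD per 12 weeks.
- One value at week 12: expected decrease −1.00.
- Values at weeks 12 and 24: −1 + E[max(Z1, Z2 − 1)] = −1 + [−Φ(−0.707) + √2·φ(0.707)] = −1 + (−0.240 + 0.439) = −0.80.
- One discontinuation value at week 4: −4/12 = −0.33.

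Among scheduled values, longer follow-up still looks better (−0.80 against −1.00). If the discontinuation sample counts, the early progressor looks best (−0.33).

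**Simulated size under the null.** From SAP 2.3: N = 180/300/540, 2:1 allocation, median PFS 6 against 12/10/8.5 months, cut-off at 70% events. Assumed: exponential PFS, uniform 24-month accrual, 12-week CA-125 sampling, log CA-125 = N(0,1) noise plus drift. Model: stratified Cox with treatment and maximum decrease per SD, 1,000 replicates per cell. Ranges cover tBRCA, HRD and ITT.

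| Values counted | Drift 0 | 0.25 | 0.5 | 1.0 |
|---|---|---|---|---|
| Scheduled + discontinuation | 0.69-0.72 | 0.85-0.86 | 0.96-0.97 | 1.08-1.11 |
| Scheduled; no post-baseline value excluded | 0.66-0.68 | 0.80 | 0.87-0.88 | 0.94-0.95 |
| Scheduled; at least one value each | 0.64-0.67 | 0.77-0.78 | 0.85-0.86 | 0.92-0.93 |
| Progression detected on the 12-week grid | 0.70-0.73 | 0.83 | 0.90 | 0.96 |

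The third row has no basis in the documents; it supplies the lower end of the flat range.

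A median split, as one categorical version, gave 0.51-0.62 when flat. At drift 1.0 it gave 0.90-0.95 without the discontinuation sample and 1.12-1.17 with it.

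**Sensitivity of the flat result.**
- 4-week sampling: 0.62-0.64. 8-week sampling: 0.64-0.67.
- Serial correlation 0.5-0.8: 0.65-0.74.
- Patient-level shift in CA-125 change (SD 1-2 noise units, assumed): 0.73-0.84.
- Baseline truncated at its mean, to imitate the below-ULN entry rule (Protocol 6.2, criterion 7): 0.61-0.66.

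**Corrected codings under the null.**
- Time-dependent running maximum: HR 0.997-1.011 per 10-point decrease with flat CA-125 and with a rise at progression; 0.96-1.02 in a smaller check (40 replicates per cell) that also covered the current-value coding.
- Time-dependent current value: 0.99-1.01 at drift 0, 0.5 and 1.0.
- Landmark at Cycle 4 Day 1 (flat): 1.00.

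**Landmark losses.** 12 weeks = 84/30.4375 = 2.76 months; loss = 1 − 2^(−2.76/median). Placebo (6 months): 27.3%. Rucaparib (12/10/8.5 months): 14.7%/17.4%/20.2%.

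**The case against.** **The consequence is small.** This stands. It is one exploratory association with no test level and no decision attached. In the null simulations the specified model rejected in 92-100% of trials with flat CA-125, at a two-sided 5% level chosen here. A reader might infer that a false-positive finding is nearly certain. The documents do not support that: the SAP sets no threshold, and at drift 1.0 rejection ran from 5% to 45%.

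**The direction is predictable.** A reader might infer that the bias can only flatter a larger decrease, because a maximum can only grow with more visits. That is true within one patient's series, but not between patients whose only values are drawn at different times. Protocol 9.5.5.2 requires a discontinuation sample, which can fall before week 12, and SAP 10.4.7 does not exclude it. The reversal above needs only that sample and a strong common rise. Calling the direction wholly unknown would also overstate the case: most scenarios lie below 1.

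**The SAP does not say all follow-up.** Correct. That is an inference from the missing window, though no other reading is offered.

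**The figures depend on an invented CA-125 model.** Correct. The documents give no CA-125 course or variability, and two plausible changes moved the flat result partly or wholly outside 0.64-0.73. The mechanism needs only repeated sampling tied to PFS, not the exact interval or laboratory.

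**The analysis is already done.** Protocol 11.3 says all endpoints were summarized when the primary endpoint was unblinded in 2017, and its list of endpoints still being collected does not include CA-125. Protocol 13.6 says that all but the long-term follow-up endpoints have been reported. This changes the remedy, not the defect.

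**Conclusion.** The point holds as a limited one. As written, SAP 10.4.7 conditions on a value that depends partly on how long the patient stayed progression-free, so its hazard ratio is open to guarantee-time bias. The size cannot be fixed from the documents. In most null scenarios a larger decrease looks falsely favourable: HR per SD about 0.64-0.73 with flat CA-125, and 0.92-0.96 with strong upward drift and no discontinuation sample. With the same drift and that sample counted, it reverses to about 1.08-1.11.

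These figures illustrate; they are not bounds. They assume independent noise and a common drift. They ignore between-patient variation in CA-125 change and the requirement that baseline be below ULN.

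A reader might infer that the treatment comparison is compromised. It is not: the primary, step-down, secondary and safety analyses do not use this covariate. Low priority.

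**What to change.** **Analysis.** In SAP 10.4.7, code the maximum decrease as a time-dependent running maximum: in each interval, the largest decrease among values drawn before that interval, with patients entering at their first post-baseline value. This keeps the SAP's own measure. Alternatively, use a landmark, for example Cycle 4 Day 1, in patients still progression-free and under follow-up, with values up to the landmark only. A time-dependent current value may be added, but it answers a separate question: current level, not depth of decrease.

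**Samples.** State whether discontinuation and unscheduled values count, and define the final visit.

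**Reporting.** Since the endpoint appears to have been summarized already, report the estimate from the SAP's model as descriptive and subject to guarantee-time bias, beside the corrected analysis, labelled as supplementary and specified after unblinding.

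**Cost.** Minor programming. SAP 10.4.1 already calls for the change at each scheduled visit, so no new data are needed, and Protocol 11.2.7.1 does not require the maximum, so no protocol change is needed.

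**Downsides.** The landmark drops about 15-27% of patients, depending on arm and population. It is also less sensitive: with a true rise of 1 noise-SD in the 12 weeks before progression, it gave HR per SD 1.23-1.27, against 1.81-1.85 for the time-dependent current value. Protocol 9.5.5.1 calls for a scan when CA-125 meets progression criteria, so some bias may remain. With scans prompted by a rise of 1-2 noise-SD, the null HR for the current value was 1.00-1.06, or 1.01-1.10 if same-day values were used; the landmark gave 1.01-1.03. The running maximum was not tested under prompted scans.
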